APPENDIX XI - PAIN/DISCOMFORT AND MEDICATION QUESTIONNAIRE

CCTG Trial HE.1

A PHASE III STUDY OF PALLIATIVE RADIOTHERAPY FOR SYMPTOMATIC HEPATOCELLULAR CARCINOMA AND LIVER METASTASES

Patient Initials: First - Middle - Last

Patient Serial #: CA _____

Institution: _____

Investigator: _____

PAIN/DISCOMFORT AND MEDICATION QUESTIONNAIRE

To the Patient:

If you have any questions about how or when to complete this questionnaire, please telephone the study nurse or CRA listed below.

(Name)

(Number)

Hours of Availability:

PATIENT QUESTIONNAIRE – PATIENT TO COMPLETE

INFORMATION AND INSTRUCTIONS FOR THE PATIENT

Thank you for participating in this research study.

This document is a questionnaire that is split up into two parts that both relate to your abdominal pain/discomfort:

Part One will be used to record your level of abdominal pain/discomfort. Please note that the questions within this document will refer to “pain”. Some patients describe abdominal “discomfort” rather than “pain”, and if this is the case, you may still complete this questionnaire. “Pain” in the questionnaire is meant to reflect abdominal “pain” or “discomfort” from your liver cancer.

Part Two will record the medication you take to treat your pain/discomfort. When you receive the questionnaire, the clinical research associate (CRA) or study nurse may have already filled in the names and doses of the medications you regularly take to treat your pain.

The next pages contain instructions to help you fill in Part One of the questionnaire and the instructions for Part Two will come later on.

You are being asked to fill in the questionnaire:

- Before you enter the study,
- about 30 days after you have started the study, and
- about 90 days after you have started the study.

Each time you fill in the questionnaire, you will be asked to give us information related to:

- your abdominal pain/discomfort and its effect on your life,
- how much medication you have taken to treat your abdominal pain/discomfort, and
- any symptoms you have and any medications you have taken for reasons other than pain/discomfort control.

If you have any questions, please ask the CRA or study nurse to help you.

Please go to the next page.

INSTRUCTIONS FOR PART ONE

Your Abdominal Pain/discomfort

We will ask you about your level of pain/discomfort in this section of the questionnaire.

To tell us about your abdominal pain/discomfort, you will be provided with a list of numbers and asked to rate your pain/discomfort by choosing **one** number from **0 (no pain/discomfort)** to **10 (pain/discomfort as bad as you can imagine)** that best describes your pain/discomfort in the last 24 hours.

This is what that question looks like:

Please rate your abdominal pain by circling the **one** number that best describes your pain at its **WORST** in the last 24 hours:

0 1 2 3 4 5 6 7 8 9 10
No pain Pain as bad as
you can imagine

Some correct and incorrect sample answers are shown below:

Correct:	0	1	2	3	4	5	6	7	8	9	10	✓
Incorrect:	0	1	2	3	4	5	6	7	8	9	10	✗
Incorrect:	0	1	2	3	4	5	6	7	8	9	10	✗

Now you are ready to fill out Part One of the questionnaire.

If you have any questions or need help, please contact the CRA or study nurse (contact information provided on the cover page).

Thank you for valuable contribution to this research study

Please go to the next page

PART ONE: PATIENT QUESTIONNAIRE – PATIENT TO COMPLETE

CRA / Study Nurse to complete below, in advance:

Please check the timing of the questionnaire:

- Baseline Questionnaire
- 30 day Post-Randomization Questionnaire
- 90 day Post-Randomization Questionnaire

[figure not shown]
NOTE: At the baseline visit, please ask the patient if they would describe their abdominal symptoms as “pain” or “discomfort”. This information will be required at the time of randomization.

Patient describes abdominal symptoms as:

[figure not shown]
- Pain
- Discomfort

Date: _____ - _____ - _____
Day *Month* *Year* Day of week: _____

[figure not shown]
1. Please rate your abdominal pain by circling the **one** number that best describes your pain at its **WORST** in the last 24 hours:

2. Please rate your abdominal pain by circling the **one** number that best describes your pain at its **LEAST** in the past 24 hours.

3. Please rate your abdominal pain by circling the **one** number that best describes your pain on **AVERAGE**.

Please go to the next page

PART ONE: PATIENT QUESTIONNAIRE – PATIENT TO COMPLETE

4. Please rate your abdominal pain by circling the one number that tells how much pain you have **RIGHT NOW.**

[figure not shown]

5. In the last 24 hours, how much relief have pain treatments or medications provided? Please circle the **one** percentage that most shows how much how much **relief** you have received.

[figure not shown]

6. Circle the **one** number that describes how, during the past 24 hours, abdominal pain has interfered with your:

[figure not shown]
A. General Activity

B. Mood

[figure not shown]
C. Walking ability

[figure not shown]
Please go to the next page

PART ONE: PATIENT QUESTIONNAIRE – PATIENT TO COMPLETE

[figure not shown]
D. Normal Work (includes both work outside the home and housework)

[figure not shown]
E. Relations with other people

F. Sleep

G. Enjoyment of life

Please go to the next page

INSTRUCTIONS FOR PART TWO

Your Pain/Discomfort Medication

To tell us how much pain/discomfort medication you took in the last 24 hours, you will be asked to fill in a table. In most cases, the CRA or study nurse will have already filled in some information about the medications you usually take for pain/discomfort. For example, if you use 10 mg tablets of Medication A and 2 mg tablets of Medication B, the table will look like this:

Name of medication	Strength of each unit of medication*	How is medication taken? **	Number of units taken ♦
Medication A	10 mg	By mouth	
Medication B	2 mg	By mouth	
♦	e.g. If you take 2 tablets in the morning and 2 tablets at night of a particular medication, you took 4 units.		
*	A unit of medication is a tablet or capsule, a millilitre (mL) of liquid, a suppository, or a patch.		
**	For example, medications can be taken by mouth, rectally, or in patch form.		

Here are some examples of how to fill in the medication table:

Ex. 1: Your doctor has prescribed 10 mg tablets of Medication A for your pain/discomfort and told you to take one tablet in the morning and one at night. Your doctor has also prescribed 2 mg tablets of Medication B and told you to take one tablet as needed when you have extra pain/discomfort (also called breakthrough pain/discomfort), up to four times a day. In the last 24 hours, you took both of the 10 mg Medication A tablets and three of the 2 mg Medication B tablets.

This is the correct way to fill in the table:

Name of medication	Strength of each unit of medication*	How is medication taken? **	Number of units taken ♦
Medication A	10 mg	By mouth	2
Medication B	2 mg	By mouth	3
♦	e.g. If you take 2 tablets in the morning and 2 tablets at night of a particular medication, you took 4 units.		
*	A unit of medication is a tablet or capsule, a millilitre (mL) of liquid, a suppository, or a patch.		
**	For example, medications can be taken by mouth, rectally, or in patch form.		

✓
✓

This is an incorrect way to fill in the table:

Name of medication	Strength of each unit of medication*	How is medication taken? **	Number of units taken ♦
Medication A	10 mg	By mouth	2
Medication B	2 mg	By mouth	1 as needed
◆ e.g. If you take 2 tablets in the morning and 2 tablets at night of a particular medication, you took 4 units.			
* A unit of medication is a tablet or capsule, a millilitre (mL) of liquid, a suppository, or a patch.			
** For example, medications can be taken by mouth, rectally, or in patch form.			

✓
✗

This is incorrect because it does not tell us exactly how much of Medication B you took before filling in the table. We need to know this to be able to get complete results for the study.

Here are some examples of how to record your medication if you use formats other than tablets:

Ex. 2: You use a patch on your skin that delivers 25 mcg of Medication C every hour. You change this patch every three days.

Name of medication	Strength of each unit of medication*	How is medication taken? **	Number of units taken ♦
Medication C	25 mcg / h	Patch	1 every 3 days
* A unit of medication is a tablet or capsule, a millilitre (mL) of liquid, a suppository, or a patch.			

✓

Ex. 3: Some pain/discomfort medications are available in liquid or syrup form. Your doctor has prescribed 2 mg/mL Medication D to you. You can take 1 to 3 mL of this liquid when you have pain/discomfort, up to six times a day. Today, you took 2 mL of Medication D just before lunch, 1 mL in the middle of the afternoon, and 3 mL just before going to bed (for a total of 6 mL).

Name of medication	Strength of each unit of medication*	How is medication taken? **	Number of units taken ♦
Medication D	2 mg / mL	By mouth	$2 + 1 + 3 = 6$
* A unit of medication is a tablet or capsule, a millilitre (mL) of liquid, a suppository, or a patch.			

✓

Please go to the next page

PART TWO: PATIENT QUESTIONNAIRE – PATIENT TO COMPLETE

Please record all the medications you took for pain/discomfort today, including what you have already taken since getting up this morning. Please make sure you record all the medication you take for breakthrough pain/discomfort, and any medication you take for pain/discomfort that wakes you up while sleeping at night.

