9.1 Compliance

Patient compliance with Pain/Discomfort and Medication Questionnaire and FACT-Hep QoL will be measured at baseline, on day 30 and on day 90. The same Pain/Discomfort and Medication Questionnaire will be used to record analgesia use in the past 24 hours at these same time points.

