10.0 CRITERIA FOR MEASUREMENT OF STUDY ENDPOINTS

10.1 Definitions

10.1.1 Evaluable for adverse events. All patients will be evaluable for adverse event evaluation from the time of randomization.

10.1.2 Evaluable for BPI response. All patients who have completed a baseline and 30 days follow-up BPI will be considered evaluable for the primary endpoint. Patients who complete a baseline and a day 90 follow-up BPI will be considered evaluable for secondary BPI endpoints. Patients from Arm 1 who cross over to Arm 2 after their day 30 assessment are evaluable for BPI response from day 30 to day 90, if they have completed their day 30 and day 90 BPI.

10.1.3 Evaluable for quality of life assessment. All patients who have completed the quality of life questionnaire at baseline and on days 30 and 90 are evaluable for the quality of life endpoint.

10.1.4 Evaluable for change in opioid analysis. All patients who have completed Pain/Discomfort and Medication Questionnaires at baseline and within 24 hours of the 30 day visit are eligible for assessment. Only analgesic use in the past 24 hours will be recorded to increase compliance. If the patient is too unwell to visit the clinic, the Pain/Discomfort and Medication Questionnaire can be completed by the study nurse following a telephone call to the patient. Note: large fluctuations in opioid use are unlikely to occur due to intolerability of medications for many patients.

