#### **4.2 Secondary Efficacy**

The secondary efficacy endpoints are:

- Proportion of patients experiencing grade  $\geq 2$  adverse events at day 30 and day 90.
- Proportion of patients alive at day 90.

- Proportion of patients achieving improvement of liver cancer pain/discomfort by  $\geq 2$  points from baseline to day 30 and day 90 in all BPI pain scores.
- Proportion of patients reporting clinically significant improvement in QoL from baseline to day 30 and day 90 as defined by a  $\geq 5$  point change in the Functional Assessment of Cancer Therapy (FACT) Hepatobiliary Subscale (FACT-HBS) and Trial Outcome Index (FACT-TOI).
- Proportion of patients achieving a 25% reduction in opioid use at 30 days (employing daily morphine equivalence scale).
- Proportion of patients achieving improvement of liver cancer pain/discomfort by  $\geq 2$  points in pain ‘intensity at worst’ AND with no increase in opioid use (employing daily morphine equivalence scale) on BPI from baseline to 30 days.

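### The medication questionnaire gives two different recall windows, the last 24 hours and 'today', so the daily opioid dose behind two secondary endpoints can depend on when the form is completed

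*Protocol*

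**What the plan says.** The protocol's intended window is clear. Section 10.1.4, on evaluability for the opioid analysis, states: "Only analgesic use in the past 24 hours will be recorded to increase compliance". Section 9.1 repeats it: "The same Pain/Discomfort and Medication Questionnaire will be used to record analgesia use in the past 24 hours at these same time points". Sections 8.2.6 and 8.3.6 say the same for each arm.

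The form in Appendix XI is not consistent with itself:

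- **Instructions for Part Two:** "To tell us how much pain/discomfort medication you took in the last 24 hours, you will be asked to fill in a table".
- **Example 1:** "In the last 24 hours, you took both of the 10 mg Medication A tablets and three of the 2 mg Medication B tablets".
- **Example 3**, whose last dose is at bedtime: "Today, you took 2 mL of Medication D just before lunch, 1 mL in the middle of the afternoon, and 3 mL just before going".
- **Answer page (Part Two: Patient Questionnaire):** "Please record all the medications you took for pain/discomfort today, including what you have already taken since getting up this morning". The next sentence adds breakthrough doses and "any medication you take for pain/discomfort that wakes you up while sleeping at night", without saying which night.

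Neither document says which wording governs. SAP 4.2 lists two endpoints that use the result. One is "Proportion of patients achieving a 25% reduction in opioid use at 30 days (employing daily morphine equivalence scale"). The other is a worst-pain improvement of at least 2 points with no increase in opioid use. SAP 7.5.4 analyses them in Tables 25 and 26 and has no rule for a form that covers less than a day.

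**The concern.** Each opioid endpoint compares a patient's own oral morphine equivalent (OME) at two visits. The comparison is fair only if both entries cover the same length of time. If 'today' is taken at its word, the entry covers the hours up to completion, and a change in completion time between baseline and day 30 looks like a change in dose.

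The documents do not hold completion time fixed. Section 9.0 lets staff help with the form at the clinic visit or complete it by telephone for a patient too unwell to attend. The opioid-evaluable set accepts forms completed within 24 hours of the day-30 visit. The visible form records the date and day of the week but no clock time, so a part-day entry cannot be scaled up afterwards.

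**Working it through.** The plan gives no figure to reproduce. The contradiction rests on wording, and the arithmetic below only sizes its consequence.

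**1. The form's own examples**

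- Example 1, full 24 hours: 2 × 10 mg + 3 × 2 mg = 26 mg. This adds the two drugs' milligrams without converting to OME, for illustration only. If the visit falls after the morning tablet and 0 to 3 breakthrough tablets, 'today' holds 10 to 16 mg. The shortfall is 1 − 16/26 = 38% to 1 − 10/26 = 62%.
- Example 3, by bedtime: 6 mL × 2 mg/mL = 12 mg. After the pre-lunch dose only, 4 mg (−67%). After the mid-afternoon dose, 6 mg (−50%).

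These shortfalls matter when the two visits cover different windows.

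**2. 'Today' read literally at both visits**

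Assumptions, none from the documents: true dose constant and taken evenly; window starts at hour *s* (07:00 or midnight); baseline hour *b* and day-30 hour *d* independent and uniform between 09:00 and 16:00.

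Apparent change = (d − s)/(b − s) − 1. A false reduction of at least 25% needs d − s ≤ 0.75(b − s).

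Single case, s = 7 and b = 14: the cut-off is d = 7 + 0.75 × 7 = 12.25, or 12:15. A 12:00 visit gives 5/7 − 1 = −29%.

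Over all pairs, the condition can be met once b ≥ b₀ = s + (9 − s)/0.75. Its probability is 0.75(16 − b₀)²/(2 × 49).

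| Start | b₀ | Probability |
|---|---|---|
| 07:00 | 9.667 | 0.375 × 6.333²/49 = 0.307 |
| midnight | 12 | 0.375 × 4²/49 = 0.122 |

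A simulation of 1,000,000 draws agrees.

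**3. Visit times within one hour of each other**

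Let d = b + e, with e uniform between −1 and 1. The condition becomes e ≤ −0.25(b − s).

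- 07:00 start: possible only for b between 09:00 and 11:00. The probability falls linearly from 0.25 to 0 over 2 of the 7 hours: 0.125 × 2/7 = 0.036.
- Midnight start: b − s is at least 9, so e ≤ −2.25 would be needed. Probability 0.

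**4. False increase**

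With even dosing, any later day-30 visit shows an increase, so by symmetry about half of patients do. Discrete dosing produces ties and lowers this.

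**5. Different windows at the two visits**

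If baseline covers 24 hours and day 30 runs from midnight to hour *h*, the apparent change is h/24 − 1: −58% at 10:00 and −33% at 16:00.

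**6. Effect on the comparison**

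If a fraction *f* of non-reducers is wrongly counted and a fraction *g* of true reducers is missed, equally in both arms, the difference between arms is multiplied by 1 − f − g. With f = 0.122 to 0.307 and g set to 0, the factor is 0.88 to 0.69. If only half of patients follow the answer page, f becomes 0.061 to 0.153 and the factor 0.94 to 0.85.

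**7. After the fix**

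With 24 hours at both visits, a constant, evenly taken dose shows 0% change at any hour.

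**The case against.** The case for leaving this alone has real weight.

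- A reader might infer that the form asks only for use since waking. It does not: time since getting up is named as an included part of 'today', and night-time doses are requested too. The window is unclear; it is not a fixed since-waking window.
- The 24-hour window is stated on the instruction page and in Example 1. A table footnote counts morning and night tablets together. Only patients who follow the last prompt over these are affected, and their share is unknown.
- The text available stops at the prompt. The blank table beneath it was not visible, and a column heading there could restate 24 hours.
- Even dosing is a strong assumption. With Example 1's morning and night tablets, visits at 12:00 and 14:00 both capture one Medication A tablet, a 0% change for that drug. Patches are recorded as a rate, so completion time does not affect them.
- Staff may pre-fill drug names, and Protocol 8.1 recommends that the nurse or CRA review the table.

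All of this limits the size. It does not remove the contradiction. The review in 8.1 is recommended only, concerns the table the patient completed, and states no window. A reader might take it for a separate 24-hour medication review that could supply the correct dose; the protocol describes none.

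**Conclusion.** The contradiction is real and sits within one form: the instructions and Example 1 say 24 hours, while the answer page and Example 3 say 'today'. Where patients follow the answer page at a daytime visit, the OME behind both secondary opioid endpoints varies with completion time.

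The illustrative rate of false reductions is about 12% to 31% with unrelated visit times and about 0% to 4% with times matched within an hour. These figures rest on even dosing, a literal reading of 'today' by every patient, and assumed clinic hours. They are not estimates for this trial, and the −29% example should not be read as a typical error.

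A reader might infer bias in favour of one arm. The documents do not support that. Both arms use the same form at the same time points, so the main expectation is misclassification that dilutes a difference. Bias would need completion times or readings of the prompt to differ by arm, and nothing shows that they do. Nor is the primary endpoint touched: BPI worst pain is asked over the last 24 hours.

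**What to change.** **For the form, if it is used again.** Change the answer-page prompt and Example 3 to 'in the last 24 hours (from this time yesterday until now)', and add a field for the time of completion. Cost: one sentence, one example and one field.

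**For this trial.** SAP 2.3 records that accrual closed on June 2, 2022, so rewording cannot help the forms already collected. In SAP 7.5.4:

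1. State that OME is meant to cover the 24 hours before completion.
2. Check baseline and day-30 entries against prescribed regimens or source records where these exist. Do not cite a separate 24-hour nurse or CRA review as the source.
3. Flag forms that appear to cover only part of a day, for example where scheduled doses are missing. With no clock time on the visible form this is a judgement, so write the rule down first and apply it without reference to treatment arm.
4. Repeat Tables 25 and 26 without the flagged patients as a sensitivity analysis, and report how many were flagged in each arm.

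Cost: a check of at most 132 forms (66 randomised patients × 2 visits) and one further run of two tables. Where no source record exists, the uncertainty remains and should be stated with the opioid results.

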## ABBREVIATIONS

AE	Adverse Event
ALT	Alanine Aminotransferase
AST	Serum Glutamic Oxaloacetic Transaminase
BPI	Brief Pain Inventory
BSC	Best Supportive Care
C. I.	Confidence Interval
CMH	Cochran-Mantel-Haenszel
CRF	Case Report Form
CTCAE	Common Terminology Criteria for Adverse Events
CCTG	Canadian Cancer Trials Group
FACT-Hep	Functional Assessment of Cancer Therapy Hepatobiliary
FACT-G	FACT-General
EWB	Emotional Well-Being
FWB	Functional Well-Being
HBS	Hepatobiliary Subscale
HCC	Hepatocellular Carcinoma
ID	Patient Identification
IN	Inevaluable
INR	International Normalized Ratio
MPV	Major Protocol Violation
NA	Not Applicable
NC	Not Computed
NCI	National Cancer Institute
OME	Oral morphine equivalents
PWB	Physical Well-Being
QLQ	Quality of Life Questionnaire
QoL	Quality of Life
RT	Radiation Therapy
TOI	Trial Outcome Index
SAS	Statistical Analysis System
SFWB	Social and Family Well-Being
STD	Standard Deviation
UNL	Upper Normal Limit
WBC	White Blood Cells

## **1. Background and Rationale**

The purpose of this analysis plan is to describe the analysis performed by the Canadian Cancer Trials Group (CCTG) for the HE.1 trial. The data are collected and cleaned by CCTG. All analyses will be performed by a senior biostatistician in CCTG and a final statistical analysis report will be prepared.

## **2. Study Description**

### **2.1 Background**

Hepatocellular carcinoma (HCC) is a disease which is often diagnosed at an advanced stage with common symptoms of pain, anorexia and fatigue are common. The liver metastases are common for patients with a variety of gastrointestinal malignancies (e.g. colorectal and pancreatic cancer), as well as non-gastrointestinal malignancies, including, melanoma, breast and gynecological cancers. For HCC and liver metastases, majority of patients become refractory to all therapy for a period of time prior to death and a substantial proportion of these patients suffer from hepatic pain. Effective palliation of hepatic pain can be challenging for these patients and there is a need for improved palliative treatments.

A radiation therapy (RT) with the use of 8 Gy in one fraction to the whole (or near-whole) liver, with an anti-emetic to prevent nausea, was shown in a phase II clinical trial resulted in a clinically meaningful improvement in average index symptom intensity assessed using the BPI one month following RT with no differences between patients with HCC and liver metastases. This treatment was also shown well tolerated. This trial was designed to prospectively compare this radiotherapy with the best supportive care (BSC) in patients with HCC and liver metastases.

